1.1 Background

Hepatocellular carcinoma is the fifth most prevalent cancer worldwide with over half a million new cases reported per year [Alterkruse et al. 2009]. Liver transplant is the only cure for hepatocellular carcinoma, with 70% 5 year survival rates [Mazzaferro et al. 1996]. However, transplant requires a relatively contained disease state (1 lesion 3 < 5 cm or up to 3 nodules < 3 cm) and the technique is limited by availability of donors [Llovet et al. 1999]. Only 30% of referred patients are eligible for surgical resection and this group is still plagued by 5 year recurrence rates higher than 70% [Bruix and Llovet 2002]. Because systemic therapies have been proven largely ineffective, embolization represents the current clinical standard for treatment of non-resectable hepatocellular carcinomas [Llovet and Bruix 2003]. Embolization of HCC can be performed via transarterial chemoembolization or radioembolization. Radioembolization is performed using TheraSpheres (BTG International). TheraSpheres consist of 20-30 µm glass beads containing yttrium-90 isotopes and are FDA approved under a Humanitarian Device Exemption for the treatment of HCC. These spheres are locally delivered via catheter through the hepatic artery to the tumor blood supply and provide a localized and sustained release of radiation. Dosages range from 110-150 Gy and radiation exposure to the surrounding liver is limited by the low penetration of the beta radiation. Yttrium-90 undergoes pure beta emission as it decays to stable zirconium-90 with a half-life of 64 hours and average energy emission of 0.94 MeV. The local beta emissions from this technique have been shown to provide therapeutic effect within the tumor [Herba et al. 1988; Houle et al. 1989]. Post-treatment, localized radioactivity is confirmed via SPECT imaging and patients are monitored for 2-6 hours before being discharged.

Treatment response of HCC to radioembolization is monitored using contrast-enhanced MRI or CT at 1 month and 3-6 months post treatment response. An earlier predictor of treatment response would be clinically beneficial as HCC patients are still eligible for chemoembolization or ablation post radioembolization. Changes in tumor perfusion have been identified as early indicators of HCC treatment response [Zocco et al 2013; Murakami et al. 2011]. Tumoral inflammation in the microenvironment may also be an early indicator of effective treatment [Serres et al. 2014]. Accurate quantification of tumoral perfusion is difficult using MRI or CT techniques, however, due to their relatively low temporal resolution.

CEUS, which has relatively high temporal resolution, has been able to identify inflammation-related changes in perfusion in other diseases, [Saevik et al. 2014] and thus may be useful in identifying inflammation following radioembolization. Ultrasound contrast agents are well tolerated and administered intravenously, making them an ideal noninvasive screening tool. Commercially available contrast imaging packages are now available on most ultrasound scanners. When insonated at sufficient acoustic pressures (MIs > 0.5), UCA undergo inertial cavitation and localized collapse [Goldberg et al. 2001]. This behavior

forms the basis of flash-replenishment imaging, in which reperfusion within an imaging plane can be repeatedly imaged using cycles of destructive pulses followed by lower MI imaging to monitor reperfusion. These flash-replenishment sequences can performed using commercially available packages that generate a higher intensity (but still well within FDA MI limits) pulse within a selected region of interest. Our group and others have also shown that blood perfusion can be quantified by measuring the rate of contrast perfusion after either a bolus injection or during flash-replenishment imaging using nonlinear CEUS [Sridharan et al. 2013; Wei et al. 1999; Gauthier 2011]. These techniques have been utilized clinically in the liver using commercially available flash-replenishment packages to quantify liver and liver tumor perfusion [Wakui et al. 2011; Shiraishi et al. 2008; Lefort, et al. 2012].

Microbubble cavitation has been demonstrated to temporarily increase both cellular and vascular permeability for improving chemotherapy delivery, and this approach has recently been used in a pilot clinical trial of patients with pancreatic cancer [Kotopoulis et al. 2013]. Importantly, localized microbubble cavitation has also been shown to sensitize tissue to radiotherapy by inducing vascular endothelial cell apoptosis [Kim et al. 2014; Al-Mahrouki et al. 2014; Tran et al. 2012; Czarnota et. al 2012]. Thus, we expect that flash-replenishment sequences that are useful for noninvasively characterizing tumor perfusion may also sensitize tumors to radiation.

The proposed agent for the current study, Optison, is a sterile non-pyrogenic suspension of encapsulated perflutren microbubbles [Goldberg et al 2001; Miller & Nanda 2004]. The contrast agent is consists of a human serum albumin shell with perflutren core and contains 5.0 - 8.0 x 10⁸ microspheres/ ml. The microbubble agent is supplied in a standard-size 3 ml vial and is prepared by manually shaking the vial. Optison is currently only approved for use in echocardiography. The agent will be used as an off-label indication for this study.

Optison Clinical Safety

Optison is well tolerated and has been used extensively in echocardiography applications [Goldberg et al 2001]. In pre-market clinical trials, Optison was administered to 279 patients. In these patients 47 (16.8%) reported at least one adverse event. Of these events, 1 was classified as serious and required antihistamines for hypersensitivity manifestations of dizziness, nausea, flushing, and temperature elevation. No deaths were reported. Of the reported adverse reactions following the use of Optison the most frequently reported were headache (5.4%), nausea and/or vomiting (4.3%), warm sensation or flushing (3.6%), and dizziness (2.5%). Additional risks associated with the contrast material are described in the attached Optison Product

insert (Appendix B). All of the non-serious reported side effects have been transient, usually lasting only a few minutes.

Table 1. Selected Adverse Events Reported in ≥ 0.5% of the Subjects who Received Optison in Controlled Clinical Studies (From Optison Product Insert).

No. of Patients Exposed to OPTISON TM	279		
No. of Patients Reporting on Adverse Event	47 (16.8%)		
Body as a Whole	38 (13.6%) 15 (5.4%) 10 (3.6%) 4 (1.4%)		
Headache			
Warm Sensation/Flushing			
Chills/fever			
Flu-like Symptoms	3 (1.1%)		
Malaise/Weakness/Fatigue	3 (1.1%)		
Cardiovascular System	12 (4.3%)		
Dizziness	7 (2.5%)		
Chest Pain	3 (1.1%)		
Digestive System	12 (4.3%)		
Nausea and/or Vomiting	12 (4.3%)		
Nervous System	3 (1.1%)		
Respiratory System	5 (1.8%)		
Dyspnea	3 (1.1%)		
Skin & Appendages	11 (3.9%)		
Injection Site Discomfort	3 (1.1%)		
Erythema	2 (0.7%)		
Special Senses	9 (3.2%)		
Altered Taste	5 (1.8%)		

Additional information concerning pre-clinical and clinical experience with Optison, including the dosing levels and reported subject complaints, can be found in the Optison Package Insert that is included as Appendix B.

1.2 Rationale

The fundamental theory behind this study is that localized UCA cavitation within the tumor vasculature will sensitize this tissue to Y-90 radiation and improve patient outcomes. Additionally, we hypothesize that quantification of UCA reperfusion following flash destructive ultrasound pulses will reflect inflammation changes, and provide an earlier predicator of radioembolization treatment response. If UCA

cavitation leads to effective sensitization of HCC to radioembolization, such an approach would improve treatment efficacy and prolong survival. If CEUS-based perfusion measurements were found to accurately predict treatment response, non-responding patients could be identified earlier and scheduled for alternative therapies such as chemoembolization or ablation (which in turn would also prolong survival).

We propose a pilot clinical trial to determine the potential of using CEUS flash-replenishment imaging for improving radioembolization therapy and predicting tumor response. The purpose of this study is to compare tumoral response in 26 patients treated with this approach to 26 patients treated via standard of care (radioembolization alone) and also to determine if quantitative CEUS data acquired from the experimental arm can predict future RECIST outcomes.

2. TRIAL OBJECTIVES

Trial Objectives: The primary objective of this trial is to:

· Characterize the ability of localized ultrasound contrast agent destruction to improve hepatocellular carcinoma (HCC) response to Y90 radioembolization.

The secondary aim of this trial is to:

• Determine if contrast-enhanced ultrasound estimated tumor perfusion can reliably predict HCC response to radioembolization 1-14 days post treatment.

3. TRIAL DESIGN

This is an open-label, randomized trial that will be conducted at one clinical site to determine if ultrasound-triggered microbubble destruction (UTMD) can be used to improve radioembolization of HCC. The subject population will be patients scheduled for radioembolization of a previously untreated HCC mass at Thomas Jefferson University. All patients will undergo single-photon emission computed tomography (SPECT) imaging as part of their standard of care to confirm effective localization of the Y90 beads. For research purposes, imaging of the chest will be performed when possible to assess extrahepatic distribution of Y90 using a planar imaging acquisition. Patients will be randomly assigned to either the experimental (UTMD + radioembolization) or control group (radioembolization alone) by the research coordinator using a random assignment generator. For patients assigned to the experimental group, the study will consist of up to three contrast-enhanced ultrasound (CEUS) exams: 1-6 hours post radioembolization, and approximately 7 and 14 days post treatment. Treatment response will be evaluated using modified response evaluation criteria in solid tumors (mRECIST) at 1 and 4 months post treatment based on the patient's clinically scheduled

contrast-enhanced MRI or CT. For patients assigned to the control group, only outcomes data will be collected (without intervention).

Study participation for those assigned to the experimental group will consist of up to three contrast-enhanced ultrasound exams. The primary measure of tumor response will be evaluated using mRECIST criteria as determined by Drs. [name] and [name] in consensus using the patients clinically scheduled 3-4 month contrast enhanced MRI or CT. As a secondary measure of tumor response, when available, changes in alpha fetal protein (AFP; collected as blood samples at 1 month as standard of care) will be recorded. Finally, each patient's progression free survival and overall survival will be monitored, although this is a tertiary outcome for this study and many patients are expected to surpass the timeline of this pilot study. Safety outcomes will be determined using changes in vital signs, observed and self-reported adverse events, changes in liver function tests (LFTs) at approximately 1 month post-embolization (preformed as part of clinical standard of care), and distribution of radioactivity on SPECT imaging. Liver function tests (LFTs) include blood tests for alanine aminotransferase, alkaline phosphatase, asparate aminotransferase, bilirubin, albumin, total protein, and prothrombin time.

3.1 Trial Duration

Individual participation for patients within the experimental arm will be limited to 3 ultrasound exams. If patients are unable to make one of the 7, or 14 day visits they will still be eligible to participate. The first CEUS exam will take place 1-6 hours post radioembolization during the patient's clinically scheduled observation period. Exams at approximately 7 and 14 days post treatment will take place during separate visits to Thomas Jefferson University. The entire ultrasound imaging protocol will require approximately 90 mins including a 30 min observation period. For patients assigned to the control arm, no additional participation will be required. Patients who receive ultrasound contrast agent will be monitored for at least 30 minutes before being discharged. The research coordinator will obtain laboratory values, imaging data, and outcomes for comparison to the experimental group (all obtained as part of the patient's clinical standard of care). Subject recruitment is expected to last 83 months (March 2017 – December 2023). Analysis and publication of results are expected to take an additional 3 months (January 2024– March 2024). Volunteer Registry Database forms will be submitted to the National Institute of Health's Office of Regulatory Compliance and Quality at the completion of the research study.

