6.5 Efficacy Assessments

The primary measure of tumor response will be evaluated using mRECIST criteria as determined by Drs. [name] and [name] in consensus using the patients clinically scheduled 3-4 month contrast enhanced MRI or CT. As a secondary measure of tumor response, changes in alpha fetal protein (AFP; collected as blood samples at 1 month as standard of care) will be recorded. Finally, each patient's progression free survival and overall survival will be monitored, although this is a tertiary outcome for this study and many patients are expected to surpass the timeline of this pilot study. Safety outcomes will be determined using changes in vital signs, observed and self-reported adverse events, and changes in liver function tests (LFTs) at 1 and month post-embolization (preformed as part of clinical standard of care). Liver function tests

(LFTs) include blood tests for alanine aminotransferase, alkaline phosphatase, asparate aminotransferase, bilirubin, albumin, total protein, and prothrombin time. SPECT imaging will be evaluated for all available cases by two blinded radiologists to evaluate if the initial UTMD session skews Therasphere distribution in the liver.

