7.2 Statistical Analyses

Qualitative findings regarding treatment response will be generated by two radiologists based on mRECIST criteria at 1 and 3-4 months post treatment (using the patient's clinically scheduled contrast-enhanced MRI or CT exams). In the event of conflicting outcome reports, outcomes will be evaluated in consensus.

All statistical analysis will be performed by [name] (SKCC Biostatistics Core and faculty member) using SAS version 9.4 (Cary, NC). Aim 1: The primary hypothesis that UTMD improves the effect of

radioembolization on tumor response in HCC patients will be tested with a non-parametric Mann-Whitney U-test of the difference in response distributions between control (radioembolization alone) and experimental group (UTMD + radioembolization), measured at 3-4 months post treatment. The outcome variable in this analysis, the mRECIST score, is treated as an ordinal variable in this analysis. **Aim 2:** To test if tumor perfusion measured by CEUS between UTMD pulses predicts HCC response to radioembolization, perfusion will be characterized in terms of contrast replenishment time intensity curves fit with a 2-parameter exponential recovery curve as described above. The relationship between the normalized profusion values from this image processing and the patients' subsequent mRECIST scores in the UTMD + radioembolization group will be evaluated with Spearman's rank order correlation.

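### Section 3.1 leaves no follow-up period between the end of recruitment and the analysis window, so on its dates the last few patients would lack their 3-4 month primary scan when that window opens

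*Combined protocol and SAP*

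**What the plan says.** Section 3.1 (Trial Duration) gives two consecutive periods. The first is recruitment: "Subject recruitment is expected to last 83 months", dated March 2017 to December 2023. The second follows at once: "Analysis and publication of results are expected to take an additional 3 months", dated January to March 2024. No follow-up period stands between them, and no data cut-off is given.

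The primary endpoint needs time to mature. Section 6.5 (Efficacy Assessments) has two physicians assess mRECIST "in consensus using the patients clinically scheduled 3-4 month contrast enhanced MRI or CT". Section 7.2 (Statistical Analyses) applies the Mann-Whitney test to response "measured at 3-4 months post treatment". Section 3 (Trial Design) gives the time points slightly differently: "mRECIST) at 1 and 4 months post treatment based on the patient's clinically scheduled".

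Sections 3 and 6.5 do expect many patients to outlast the study timeline, but they say so of progression-free and overall survival, which are tertiary. No such allowance is made for the primary scan, and no rule is given for patients who lack it.

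**The concern.** The calendar and the endpoint definition do not fit together. If recruitment runs to the end of December 2023 and analysis starts in January 2024, anyone treated in the preceding three to four months has not yet reached the primary time point. Treatment follows enrolment, so any delay between the two widens the gap.

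Section 7.2.1 asks for 52 patients randomised to each group to reach 85% power and states no allowance for missing outcomes, so each unread scan comes straight off the planned information. The trial is also open-label. Without a cut-off, the choice to wait for late scans or to analyse without them would be made after the data have begun to be seen.

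**Working it through.** **Inputs**
- Recruitment March 2017 to December 2023; analysis and publication January to March 2024 (section 3.1).
- Primary scan at 3-4 months after treatment (sections 6.5 and 7.2); 4 months in section 3. Section 1.1 describes routine monitoring at 3-6 months. I use 3-4 months because the primary analysis does.
- 104 patients, 52 per group (synopsis and section 7.2.1).
- Relative effect 0.6, 5% type I error, 85% power (section 7.2.1). Sidedness is not stated for Aim 1; I assume two-sided.
- About 52 HCC patients a year treated with yttrium-90 at the site (section 6.1).
- Assumptions: even accrual, and treatment in the month of recruitment.

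**Step 1: length of recruitment.** March to December 2017 is 10 months and 2018 to 2023 is 72 months. 10 + 72 = 82 inclusive months, against 83 stated. This slip does not affect what follows.

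**Step 2: scan dates for late patients.**

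| Treated | 3-month scan | 4-month scan |
|---|---|---|
| 31 Aug 2023 | 30 Nov 2023 | 31 Dec 2023 |
| 1 Sep 2023 | 1 Dec 2023 | 1 Jan 2024 |
| 1 Oct 2023 | 1 Jan 2024 | 1 Feb 2024 |
| 30 Nov 2023 | 29 Feb 2024 | 30 Mar 2024 |
| 1 Dec 2023 | 1 Mar 2024 | 1 Apr 2024 |
| 31 Dec 2023 | 31 Mar 2024 | 30 Apr 2024 |

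When the window opens on 1 January 2024, patients treated from 1 October (3-month scan) or 1 September (4-month scan) have not been read. By 31 March 2024 everyone treated through November can have been scanned. Of the December patients, those scanned at 3 months are in and those scanned at 4 months are not.

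**Step 3: number of patients.** 104/82 = 1.27 a month.
- At 1 January: 3 × 1.27 = 3.8 to 4 × 1.27 = 5.1, so about 4-5 patients.
- At 31 March: up to 1 × 1.27, so about 1 patient.

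**Step 4: power.** First the plan's own figure. I use a normal approximation, with n per group multiplied by the Mann-Whitney relative efficiency 3/π = 0.955:

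Power = Φ(0.6 × √(0.955n/2) − 1.96)

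- n = 52: Φ(2.990 − 1.960) = Φ(1.030) = 84.8%, which reproduces the stated 85%.
- 1 lost (n = 51.5): 84.5%.
- 4 lost (n = 50): 83.4%.
- 5 lost (n = 49.5): 83.1%.

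**Step 5: upper bound on late accrual.** If every yttrium-90 HCC patient enrolled at the end, the rate would be 52/12 = 4.33 a month. Then 3 × 4.33 = 13 to 4 × 4.33 = 17.3 patients would lack the scan on 1 January, and power would be 79.9% to 77.9%. This is a ceiling, since the site count is taken before the eligibility criteria and consent.

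**The case against.** The best reply is that section 3.1 gives expectations, not rules. It sets one combined period for analysis and publication, names no data lock, and nowhere says that patients without a scan are dropped. Section 7.2 defines the comparison by time since treatment and names no calendar date. One Mann-Whitney test takes little time and could be run at the end of March 2024, when patients treated through November could all be included.

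Much of this stands. A reader might infer that the trial cannot obtain the primary endpoint for all 104 patients; the documents do not support that, because nothing obliges the team to analyse on 1 January. A reader might also infer that every December 2023 patient is scanned at or after the end of the timeline. That is wrong too: a patient treated on 1 December and scanned at 3 months is read on 1 March, well inside the window. Nor is short survival follow-up a separate fault, since the protocol already calls those outcomes tertiary and expects patients to outlast the timeline.

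The reply does not remove the gap. Running the test at the end of March leaves no time for the analysis and publication that the same window is meant to hold, and still misses December patients scanned later than about 3 months. The timeline allowance for survival does not extend to the primary scan. The completion criteria in section 6.7 do not help either: they rest on ultrasound exams in one arm and on consent in the other, not on the primary scan.

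**Conclusion.** The concern holds as a contradiction between the stated dates and the primary endpoint, with a modest effect. About 4-5 of 104 patients would lack the primary scan when the analysis window opens, and about 1 might lack it when the window closes: roughly 1-5% of the sample. If all 4-5 were left out, power would fall from about 85% to about 83%.

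These sizes rest on even accrual and on treatment in the month of recruitment. The documents give no accrual data, so a late surge is possible but unsupported, and the 78-80% power at full patient flow should be read only as a bound. The effect does not threaten the trial, but it is avoidable and should be corrected. The 83-month figure is a clerical matter with no consequence for the analysis.

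**What to change.** In section 3.1, separate recruitment, follow-up and analysis. State that the primary analysis is run only after the last randomised patient has passed the end of the 4-month scan window, and say how patients still without a scan at that point are handled. With treatment to 31 December 2023 the cut-off is about the end of April 2024. Keeping three months for analysis and publication moves the end to about the end of July 2024. Use the same scan window in section 3 as in sections 6.5 and 7.2, and change 83 months to 82 or correct the dates.

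If the March 2024 end is fixed, close recruitment so that the last treatment falls by about 31 August 2023.

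Either way the cost is a dates amendment and about four months, as a later analysis or an earlier close; no visits are added. The two are not equal for power. At 1.27 patients a month, closing four months early forgoes 4 × 1.27 = 5.1 patients (104 − 5 = 99) unless the target has been met by then. Moving the analysis keeps them, so it is the better choice if the end date can move.

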4. TRIAL POPULATION

Trial Population: This trial will consist of up to 104 adults (18 years of age or older) undergoing radioembolization of a previously untreated HCC mass less than 6 cm in diameter.

Subjects eligible for trial enrollment will be identified by the co-investigators from their patient population of subjects being seen for radioembolization of HCC. These patients will be accrued from the Hepatology department, as well as from the HCC Multidisciplinary Tumor Board of the Kimmel Cancer Center at Thomas Jefferson University. A research coordinator will explain the study to the patient. The patient will be given time to consider the risks and benefits of the study and ask questions about participation. The coordinator will review the consent form with the patient and then the patient will be given the form to review. The patient, coordinator, and a study investigator will all sign the consent form. The patient will be given a copy of the signed consent form for their records.

